#### 8.2.2.15 Other toxicities

- For **all other grade 3 toxicities considered at least possibly related to treatment**, omit the responsible drug(s) until toxicity improves to  $\leq$  grade 1, then resume the responsible drug(s) at the next lower dose level.
- For **all other grade 4 toxicities considered at least possibly related to treatment**, discontinue the responsible drug(s). If the responsible drug is vemurafenib, discontinue both cobimetinib and vemurafenib. The exception is hyperglycemia (see [Section 8.2.4](#)) or electrolyte abnormalities that can be managed with medical therapy, where the responsible drugs do not need to be discontinued if the adverse event is adequately managed.

### 8.2.3 Dose modifications for obese patients

There is no clearly documented adverse impact of treatment of obese patients when dosing is performed according to actual body weight. Therefore, all dosing is to be determined solely by actual weight without any modification unless explicitly described in the protocol. This will eliminate the risk of calculation error and the possible introduction of variability in dose administration. Failure to use actual body weight in the calculation of drug dosages will be considered a major protocol deviation. Physicians who are uncomfortable with calculating doses based on actual body weight should recognize that doing otherwise would be a protocol violation. Physicians may consult the published guidelines of the American Society of Clinical Oncology Appropriate Chemotherapy Dosing for Obese Adult Patients with Cancer: American Society of Clinical Oncology Clinical Practice Guideline. J Clin Oncol 30(13): 1553-1561, 2012.

### 8.2.4 Hyperglycemia and metabolic effects

Patients should be instructed to report symptoms associated with hyperglycemia such as thirst, frequent urination, and blurred vision. Use of oral anti-hyperglycemic agents, such as metformin, for patients experiencing Grade  $\geq 2$  hyperglycemia may be implemented. For Grade 3 or greater hyperglycemia, consider increasing dose of anti-hyperglycemic agents, such as metformin, and initiating insulin. Anti-hyperglycemic agents should be used to control severe hyperglycemia per institutional standard of care. Recommended management of hyperglycemia:

- For Grade 2 or greater hyperglycemia, consider initiating oral glucose lowering medication such as metformin
- For Grade 3 or greater hyperglycemia, hydration status should be clinically assessed. If clinical assessment is consistent with dehydration, fluids should be given as clinically appropriate. If patient is asymptomatic, consider increasing oral glucose lowering medication. If patient is symptomatic, rapid/short acting insulin should be initiated according to institution sliding scale coverage as per institutional guidelines, and consider increasing oral glucose lowering medication. For persistent Grade 3 or greater hyperglycemia, please consult with endocrinologist. Grade 4 hyperglycemia should lead to agent discontinuation only if it does not respond to initial medical treatment with appropriate glucose lowering medication.

## 9.0 ADVERSE EVENTS

The prompt reporting of adverse events is the responsibility of each investigator engaged in clinical research, as required by Federal Regulations. Adverse events must be described and graded using the terminology and grading categories defined in the NCI's Common Terminology Criteria for Adverse Events (CTCAE), Version 4.0 for dose modifications and adverse event reporting through Rave. However, CTCAE v5.0 must be used for serious AE reporting through CTEP-AERS as of April 1, 2018. The CTCAE is available at [REDACTED] Attribution to protocol treatment for each adverse event must be determined by the investigator and reported on the required forms. Please refer the NCI Guidelines: Adverse Event Reporting Requirements for further details on AE reporting procedures.

### 9.1 Routine adverse event reporting

Adverse event data collection and reporting, which are required as part of every clinical trial are done to ensure the safety of patients enrolled in the studies as well as those who will enroll in future studies using similar agents. Adverse events are reported in a routine manner at scheduled times according to the study calendar in [Section 5.0](#). For this trial, the form "Adverse Events: Solicited" is used for routine AE reporting in Rave.

**Solicited Adverse Events:** The following adverse events are considered "expected" and their presence/absence should be solicited, and severity graded, at baseline and for each cycle of treatment.

CTCAE v4.0 Term	CTCAE v4.0 System Organ Class (SOC)
Blurred vision	Eye Disorders
Diarrhea	Gastrointestinal disorders
Fatigue	General disorders and administration site conditions
Alanine aminotransferase increased	Investigations
Aspartate aminotransferase increased	Investigations
CPK increased	Investigations
Photosensitivity	Skin and subcutaneous tissue disorders
Rash maculo-papular	Skin and subcutaneous tissue disorders

### 9.2 CTCAE routine reporting requirements

In addition to the solicited adverse events listed in [Section 9.1](#), the following table outlines the combinations of time points, grades and attributions of AEs that require routine reporting to the Alliance Statistics and Data Center. Questions about routine reporting should be directed to the Data Manager.

**\*Combinations of CTCAE Grade & Attribution Required for Routine AE Data Submission on Case Report Forms (CRFs)**

Attribution	Grade 1	Grade 2	Grade 3	Grade 4	Grade 5
Unrelated			a	a	a

Unlikely			a	a	a
Possible		a	a, b	a, b	a, b
Probable		a	a, b	a, b	a, b
Definite		a	a, b	a, b	a, b

- a) Adverse Events: Other CRF - Applies to AEs occurring between registration and within 30 days of the patient's last treatment date, or as part of the Clinical Follow-Up Phase.
- b) Adverse Events: Late CRF - Applies to AEs occurring greater than 30 days after the patient's last treatment date.

### 9.3 AEs of special interest

#### 9.3.1 AEs of special interest related to radiotherapy

In addition to routine reporting requirements as outlined in [Sections 9.1](#) and [9.2](#), the following adverse events of special interest must be reported via routine event reporting for any grade regardless of attribution, and may necessitate reporting via CTEP-AERS (see [Section 9.4](#)). These adverse events must be reported for patients on Cohort A who receive radiation therapy after treatment with vemurafenib and cobimetinib.

Adverse Events: Late CRF, as part of Clinical Follow-up, should be used to report AEs during radiotherapy occurring greater than 30 days after the patient's last treatment date.

CTCAE v4.0 Term	CTCAE v4.0 System Organ Class (SOC)
Hearing impaired	Ear and labyrinth disorders
External ear inflammation	Ear and labyrinth disorders
Endocrine disorders- Other, specify	Endocrine disorders
Retinopathy	Eye disorders
Optic nerve disorder	Eye disorders
Nausea	Gastrointestinal Disorders
Vomiting	Gastrointestinal Disorders
Dermatitis radiation	Injury, poisoning and procedural complications
Wound dehiscence	Injury, poisoning and procedural complications
Radiation recall reaction (dermatologic)	Injury, poisoning and procedural complications
Cognitive disturbance	Nervous system disorders
Edema cerebral	Nervous system disorders
Central nervous system necrosis	Nervous system disorders
Ischemia cerebrovascular	Nervous system disorders
Alopecia	Skin and subcutaneous tissue disorders

### 9.3.2 AEs of special interest related to vemurafenib + cobimetinib

In addition to routine reporting requirements as outlined in [Sections 9.1](#) and [9.2](#), the following adverse events of special interest must be reported via routine event reporting regardless of attribution, and may necessitate reporting via CTEP-AERS (see [Section 9.4](#)). If a grade is not specified in the table below, then reporting is required for any grade of that AE. These events must be reported in Rave in same time frame as serious adverse events (see table in [Section 9.4](#)).

Adverse Events: Other CRF should be used to report AEs occurring between registration and within 30 days of the patient's last treatment date.

Adverse Events: Late CRF should be used to report AEs occurring greater than 30 days after the patient's last treatment date.

CTCAE v4.0 Term	CTCAE v4.0 System Organ Class (SOC)
Grade $\geq$ 2 Heart failure	Cardiac disorders
Grade $\geq$ 2 Left ventricular systolic dysfunction	Cardiac disorders
Optic nerve disorder	Eye disorders
Retinal detachment (including neurosensory retinal detachment)	Eye disorders
Retinal vascular disorder (including retinal vein occlusion)	Eye disorders
Retinopathy (including serous retinopathy and central serous chorioretinopathy)	Eye disorders
Eye disorders (other) – (including retinal pigment epithelium detachment, or any other eye disorders)	Eye disorders
Events suggestive of Drug Induced Liver Injury (report as Hepatobiliary disorders – Other, specify)	Hepatobiliary disorders
Grade $\geq$ 2 Ejection fraction decreased	Investigations
Grade $\geq$ 3 Electrocardiogram QT corrected interval prolonged	
Grade $\geq$ 3 Hemorrhage event (report per specific CTCAE hemorrhage location)	Eye disorders Gastrointestinal disorders Hepatobiliary disorders Injury, poisoning and procedural complications Renal and urinary disorders Reproductive system and breast disorders Respiratory, thoracic and mediastinal disorders
Intracranial hemorrhage	Nervous system disorders

Treatment related secondary malignancy	Neoplasms benign, malignant and unspecified (incl cysts and polyps)
Neoplasms benign, malignant and unspecified (incl cysts and polyps) – Other, including: 
 
• New or worsening malignancies
 
• Non-cutaneous squamous cell carcinoma
 
• Skin cancers
 
• Gastrointestinal polyps
 
	Neoplasms benign, malignant and unspecified (incl cysts and polyps)

#### 9.4 Expedited adverse event reporting (CTEP-AERS)

Investigators are required by Federal Regulations to report serious adverse events as defined in the table below. Alliance investigators are required to notify the Alliance Central Protocol Operations Program, the Study Chair, and their Institutional Review Board if a patient has a reportable serious adverse event. CTCAE term (AE description) and grade: The descriptions and grading scales found in the revised NCI Common Terminology Criteria for Adverse Events (CTCAE) version 4.0 will be utilized until March 31, 2018 for expedited AE reporting. CTCAE version 5.0 will be utilized for AE reporting via CTEP-AERS beginning April 1, 2018. All appropriate treatment areas should have access to a copy of the CTCAE version 5.0 and CTCAE version 4.0. A copy of the CTCAE version 5.0 can be downloaded from the CTEP web site

All reactions determined to be “reportable” in an expedited manner must be reported using the Cancer Therapy Evaluation Program Adverse Event Reporting System (CTEP-AERS), accessed via the CTEP Web site.

For further information on the NCI requirements for SAE reporting, please refer to the ‘NCI Guidelines for Investigators: Adverse Event Reporting Requirements’ document published by the NCI.

**Note: All deaths on study require both routine and expedited reporting regardless of causality. Attribution to treatment or other cause should be provided.**

##### 9.4.1 Expedited reporting requirements for adverse events that occur on studies under an Alliance-IND/IDE within 30 days of the last administration of the investigational agent/intervention 

#### FDA REPORTING REQUIREMENTS FOR SERIOUS ADVERSE EVENTS (21 CFR Part 312)

**NOTE:** Investigators **MUST** immediately report to the sponsor (NCI) **ANY** Serious Adverse Events, whether or not they are considered related to the investigational agent(s)/intervention (21 CFR 312.64)

An adverse event is considered serious if it results in **ANY** of the following outcomes:

- 1) Death
- 2) A life-threatening adverse event
- 3) An adverse event that results in inpatient hospitalization or prolongation of existing hospitalization for ≥ 24 hours
- 4) A persistent or significant incapacity or substantial disruption of the ability to conduct normal life functions
- 5) A congenital anomaly/birth defect.
- 6) Important Medical Events (IME) that may not result in death, be life threatening, or require hospitalization may be considered serious when, based upon medical judgment, they may jeopardize the patient or subject

and may require medical or surgical intervention to prevent one of the outcomes listed in this definition. (FDA, 21 CFR 312.32; ICH E2A and ICH E6).

**ALL SERIOUS** adverse events that meet the above criteria **MUST** be immediately reported to the NCI via AdEERS within the timeframes detailed in the table below.

Hospitalization	Grade 1 and Grade 2 Timeframes	Grade 3 – 5 Timeframes
Resulting in Hospitalization ≥ 24 hrs	10 Calendar Days	24-Hour 5 Calendar Days
Not resulting in Hospitalization ≥ 24 hrs	Not required	

**NOTE:** Protocol specific exceptions to expedited reporting of serious adverse events are outlined in [Section 9.4.2](#).

**Expedited AE reporting timelines are defined as:**

- “24-Hour; 5 Calendar Days” - The AE must initially be reported via AdEERS within 24 hours of learning of the AE, followed by a complete expedited report within 5 calendar days of the initial 24-hour report.
- “10 Calendar Days” - A complete expedited report on the AE must be submitted within 10 calendar days of learning of the AE.

Serious adverse events that occur more than 30 days after the last administration of investigational agent/intervention and have an attribution of possible, probable, or definite require reporting as follows:

**Expedited 24-hour notification followed by complete report within 5 calendar days for:**

- All Grade 3, 4, and Grade 5 AEs

**Expedited 10 calendar day reports for:**

- Grade 2 AEs resulting in hospitalization or prolongation of hospitalization

- Expedited AE reporting timelines defined:
  - “24 hours; 5 calendar days” – The investigator must initially report the AE via CTEP-AERS ≤ 24 hours of learning of the event followed by a complete CTEP-AERS report ≤ 5 calendar days of the initial 24-hour report.
  - “10 calendar days” - A complete CTEP-AERS report on the AE must be submitted ≤ 10 calendar days of the investigator learning of the event.
- Use the NCI protocol number and the protocol-specific patient ID provided during trial registration on all reports.

#### **9.4.2 Additional instructions or exclusions to CTEP-AERS expedited reporting requirements for phase 2 and 3 trials utilizing an agent under a non-CTEP IND:**

- All adverse events reported via CTEP-AERS (i.e., serious adverse events) should also be forwarded to your local IRB.
- Grade 3/4 hematosuppression and hospitalization resulting from such do not require CTEP-AERS, but should be submitted as part of study results.
- Grade 1-3 fatigue does not require expedited reporting via CTEP-AERS reporting, but should be reported via routine AE reporting.
- Grade 1-3 alopecia and hospitalization resulting from such do not require expedited reporting via CTEP-AERS reporting, but should be reported via routine AE reporting.

- Grade 1-3 alopecia does not require expedited reporting via CTEP-AERS reporting, but should be reported via routine AE reporting
- Grade 1-3 nausea, abdominal pain, vomiting, constipation or diarrhea does not require expedited reporting via CTEP-AERS reporting, but should be reported via routine AE reporting
- Grade 1-2 dysphagia, mucositis oral, anorexia, or weight loss do not require expedited reporting via CTEP-AERS reporting, but should be reported via routine AE reporting.
- Grade 1-2 headache or dizziness does not require expedited reporting via CTEP-AERS reporting, but should be reported via routine AE reporting
- Grade 1-2 fever or chills does not require expedited reporting via CTEP-AERS reporting, but should be reported via routine AE reporting.
- Grade 1-2 arthralgia, back pain, myalgia, pain in extremity, or palmar-plantar erythrodysesthesia syndrome does not require expedited reporting via CTEP-AERS reporting, but should be reported via routine AE reporting.
- Grade 1-2 peripheral motor neuropathy or peripheral sensory neuropathy does not require expedited reporting via CTEP-AERS reporting, but should be reported via routine AE reporting.
- Grade 1-2 generalized edema or edema limbs does not require expedited reporting via CTEP-AERS reporting, but should be reported via routine AE reporting.
- Grade 1-2 acute kidney injury does not require expedited reporting via CTEP-AERS reporting, but should be reported via routine AE reporting.
- Grade 1-2 electrocardiogram QT corrected interval prolonged does not require expedited reporting via CTEP-AERS reporting, but should be reported via routine AE reporting.
- Grade 1-2 photosensitivity or eye disorders-other does not require expedited reporting via CTEP-AERS reporting, but should be reported via routine AE reporting.
- Grade 1-2 serum amylase increased or hyperglycemia do not require expedited reporting via CTEP-AERS reporting, but should be reported via routine AE reporting.
- Grade 1-2 pruritis, skin papilloma, hyperkeratosis, dry skin, rash acneiform, or rash maculopapular do not require expedited reporting via CTEP-AERS reporting, but should be reported via routine AE reporting.
- Grade 1-2 skin and subcutaneous tissue disorders-Other (including actinic keratosis, keratosis pilaris) does not require expedited reporting via CTEP-AERS reporting, but should be reported via routine AE reporting.
- Grade 1-2 alanine amino transferase increased, alkaline phosphatase increased, aspartate aminotransferase increased, CPK increased, or GGT increased do not require expedited reporting via CTEP-AERS reporting, but should be reported via routine AE reporting.
- Grade 1-2 anemia, neutrophil count decreased, hyponatremia, or hypophosphatemia do not require expedited reporting via CTEP-AERS reporting, but should be reported via routine AE reporting.
- All new malignancies must be reported via CTEP-AERS whether or not they are thought to be related to either previous or current treatment. All new malignancies should be reported, i.e. solid tumors (including non-melanoma skin malignancies), hematologic malignancies, myelodysplastic syndrome/acute myelogenous leukemia, and in situ tumors. In CTCAE v4.0, secondary malignancies may be reported as one of the

following three options: 1) Leukemia secondary to oncology chemotherapy, 2) Myelodysplastic syndrome, or 3) Treatment-related secondary malignancy. Any malignancy possibly related to cancer treatment (including AML/MDS) should also be reported via the routine reporting mechanisms outlined in each protocol. Second malignancies, which are unrelated to the treatment of a prior malignancy (and are **NOT** a metastasis from the initial malignancy), require **ONLY** routine reporting unless otherwise specified. Whenever possible, the CTEP-AERS reports for new malignancies should include tumor pathology, history of prior tumors, prior treatment/current treatment including duration, any associated risk factors or evidence regarding how long the new malignancy may have been present, when and how the new malignancy was detected, molecular characterization or cytogenetics of the original tumor (if available) and of any new tumor, and new malignancy treatment and outcome, if available.

- CTEP-AERS reports should be submitted electronically.
- All pregnancies and suspected pregnancies occurring in female patients or in the partner of a male patient during therapy or within 28 days after completion of treatment on A071102 must be reporting via CTEP-AERS. In CTCAE version 5.0, use the event term, “*pregnancy, puerperium, and perinatal condition-other, fetal exposure (grade 4)*”.
  - a. CTEP-AERS reports should be amended upon completion of the pregnancy to report pregnancy outcome (e.g. normal, spontaneous abortion, therapeutic abortion, congenital abnormalities).
  - b. Any Pregnancy loss should be reported expeditiously, as Grade 4 “Pregnancy loss” under the Pregnancy, puerperium and perinatal conditions SOC. A Pregnancy loss should NOT be reported as a Grade 5 event under the Pregnancy, puerperium and perinatal conditions SOC, as currently CTEPAERS recognizes this event as a patient death.
  - c. The CTEP-AERS report should be amended for any neonatal deaths or complications occurring within 28 days of birth independent of attribution. Infant deaths occurring after 28 days considered to be related to in utero exposure to the agents used in this trial should be reported via CTEP AERS. A neonatal death should be reported expeditiously as Grade 4, “Death neonatal” under the General disorders and administration SOC.
- Death due to progressive disease should be reported as Grade 5 “Disease progression” in the system organ class (SOC) “General disorders and administration site conditions.” Evidence that the death was a manifestation of underlying disease (e.g., radiological changes suggesting tumor growth or progression: clinical deterioration associated with a disease process) should be submitted.

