#### 3.1 On-study guidelines

This clinical trial can fulfill its objectives only if patients appropriate for this trial are enrolled. All relevant medical and other considerations should be taken into account when deciding whether this protocol is appropriate for a particular patient. Physicians should consider the risks and benefits of any therapy, and therefore only enroll patients for whom this treatment is appropriate.

Physicians should consider whether any of the following may render the patient inappropriate for this protocol:

- Psychiatric illness which would prevent the patient from giving informed consent.
- Medical condition such as uncontrolled infection (including HIV), uncontrolled diabetes mellitus or cardiac disease which, in the opinion of the treating physician, would make this protocol unreasonably hazardous for the patient.
- Patients with a “currently active” second malignancy other than non-melanoma skin cancers. Patients are not considered to have a “currently active” malignancy if they have completed therapy and are free of disease for  $\geq 3$  years.
- Patients who cannot swallow oral formulations of the agents.

In addition:

- As there is evidence that vemurafenib and cobimetinib may decrease the concentration of hormonal contraceptives (such as birth control pills), women and men of reproductive potential should agree to use two methods of birth control throughout their participation in this study (and for six months after discontinuation of study drugs) due to the teratogenic potential of the therapy utilized in this trial. Appropriate methods of birth control include abstinence, oral contraceptives, implantable hormonal contraceptives or double barrier method (diaphragm plus condom). Physicians should discuss the appropriate methods of birth control, or pregnancy prevention, with the patient prior to study enrollment.

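### The two-method contraception rule in section 3.1 can be met by two hormonal methods that the protocol says the study drugs may weaken, and the pregnancy-reporting rule in section 9.4.2 names the wrong study

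*Combined protocol and SAP*

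**What the plan says.** Section 3.1 (On-study guidelines) asks women and men of reproductive potential to agree to two methods of birth control throughout participation, "and for six months after discontinuation of study drugs) due to the teratogenic potential of the therapy utilized in this trial". The same bullet opens with a reason for asking for two: "there is evidence that vemurafenib and cobimetinib may decrease the concentration of hormonal contraceptives". It then says: "Appropriate methods of birth control include abstinence, oral contraceptives, implantable hormonal contraceptives or double barrier method", explains double barrier as diaphragm plus condom, and tells physicians to discuss suitable methods before enrolment. It nowhere says that one of the two must be non-hormonal.

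Section 9.4.2 contains the only rule in the available text that makes a pregnancy reportable in itself. Pregnancies in female patients or in partners of male patients, during therapy or "within 28 days after completion of treatment on A071102 must be reporting via CTEP-AERS". Elsewhere the protocol identifies itself as A071601 (for example sections 4.2.1 and 4.6).

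Other parts of section 9 bear on late pregnancies:

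- Section 9.4.1 lists "A congenital anomaly/birth defect" among the outcomes that make an event serious.
- Its footnote requires reports of serious events that "occur more than 30 days after the last administration of investigational agent/intervention and have an attribution of possible, probable, or definite".
- Section 9.2 collects qualifying adverse events within 30 days of last treatment "or as part of the Clinical Follow-Up Phase". It adds: "Adverse Events: Late CRF - Applies to AEs occurring greater than 30 days after" the last treatment date.
- Section 9.4.2, sub-items b and c, covers any pregnancy loss and infant deaths related to in utero exposure.

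**The concern.** The contraception rule has a stated purpose: to keep protection adequate when the drugs may weaken hormonal methods. A rule that can be met by two hormonal methods does not secure that purpose, because one drug effect may weaken both at once. This matters most during therapy, when exposure is highest. The section 5.0 calendar asks for pregnancy tests within 7 days before registration and within 7 days before starting drug, and schedules none on treatment. Cohort B may stay on drug until progression (section 12.1.1). Contraception is therefore the main written safeguard while patients are on drug.

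The wrong study number is a smaller matter, but it stands in an operative safety rule. Taken literally, the post-treatment part of the duty belongs to another trial.

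The difference between 28 days and six months also catches the eye. A site that has advised against conception for six months might reasonably ask whether a pregnancy beginning in month three should be reported.

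**Working it through.** **Contraception rule.** Section 3.1 names four methods: abstinence, oral contraceptives, implantable hormonal contraceptives and double barrier. Two of the four are hormonal. Four methods give 4 × 3 / 2 = 6 pairs, and exactly one of these, oral plus implant, is wholly hormonal. It satisfies the two-method wording, and it is the one listed pair in which both members belong to the class the bullet warns about. A non-hormonal requirement would remove that pair and leave the other five. The documents give no size for the reduction in hormone levels, so the loss of protection cannot be quantified. The planned enrolment table (section 13.8) has 19 + 3 = 22 women and 12 + 2 = 14 men, all adults; the documents do not say how many are of reproductive potential.

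**Study number.** A071102 appears in the 9.4.2 pregnancy rule and nowhere else in the text provided. This is current text, not an amendment log.

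**Reporting window, in calendar time.** Take six months as 183 days.

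- Days outside the 28-day rule: 183 − 28 = 155
- Share: 155 / 183 = 84.7%

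**Reporting window, in exposure time.** Five half-lives, in days, are 5 × t½ / 24.

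| Drug and half-life | Source | Five half-lives end at |
|---|---|---|
| Vemurafenib 57 h | 10.1 | day 11.9 |
| Vemurafenib 90 h (mean) | 1.7.1 | day 18.8 |
| Vemurafenib 120 h (upper limit) | 10.1 | day 25.0 |
| Vemurafenib 145 h (upper limit) | 1.7.1 | day 30.2 |
| Cobimetinib 96 h (upper limit) | 1.7.2, study NO25395 | day 20.0 |

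Vemurafenib remaining at day 28 (672 h) is 2^(−672/t½): 4.0% at 145 h, 2.1% at 120 h, 0.6% at 90 h and 0.03% at 57 h. In the slowest case, 30.2 − 28 = 2.2 of the 155 days fall before five half-lives. The remaining 183 − 30.2 = 152.8 days (152.8 / 155 = 98.6%) fall after.

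**Expected late pregnancies.** The documents give no fertility figures, so these inputs are assumptions: 2 to 20 of the 36 patients or their partners able to conceive (the low end allows for the panhypopituitarism described in section 1.1), and 1% to 5% conceiving per year on contraception. With 155 / 365 = 0.425 years:

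- Low: 2 × 0.01 × 0.425 = 0.008
- High: 20 × 0.05 × 0.425 = 0.42

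**The case against.** On contraception, the strongest reply is that the rule should be read for its purpose. Reduced hormone levels are a reason given for wanting two methods, the list is not exhaustive, nothing in it endorses a pill with an implant, and the physician must discuss the choice. Section 3.1 is also a guideline, not a numbered eligibility criterion. All of that is true. A reader should not infer that the protocol recommends a wholly hormonal pair; it only fails to exclude one. That omission stands, because a physician who follows the text can accept the pair.

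On the study number, a carry-over slip is the natural explanation, and a site is unlikely to conclude that it has no duty in this trial. That is fair, and it makes the correction editorial.

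On the window, a reader might infer that the protocol contradicts itself and leaves 85% of the risk period unmonitored. The documents do not support this. Contraception advice is precautionary, while the 9.4.2 duty is an expedited report under a fetal-exposure term, which can sensibly follow drug clearance. Birth defects, late serious events attributed to treatment, pregnancy losses and related infant deaths have their own routes, though some need an attribution or a literal reading. What is left is mainly a late pregnancy that nobody treats as an adverse event and that is ongoing or ends normally. Section 9.0 also sends sites to NCI reporting guidelines that were not available here and may add a rule.

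**Conclusion.** The point holds in limited form, at low severity. Section 3.1 permits, by its wording, a pair of methods that its own warning says may both be weakened, during full drug exposure and without scheduled on-treatment pregnancy tests. Section 9.4.2 names the wrong study. Both should be corrected.

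The window is an optional alignment. The 155 uncovered days are a calendar figure; at least 98.6% of them follow five half-lives even at the longest half-life quoted, and the expected number of late pregnancies is well under one on the assumed inputs. The conclusion rests on the visible text, since consent pages were removed and the NCI guidelines could not be consulted. Sample size, power and the primary analysis are untouched.

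**What to change.** 1. In section 3.1, add: *At least one of the two methods must be non-hormonal.* Cost: a slightly narrower choice of contraceptives.
2. In section 9.4.2, replace A071102 with A071601 in the pregnancy rule, and correct the verb to *reported*.
3. Optionally, extend the 9.4.2 window to six months after the last dose of study drug. Cost: a few extra expedited reports, mostly of pregnancies begun after clearance.

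All three need only amendment wording and a site notice, with no added visit. Capture under item 3 would be passive. The post-treatment visit falls at 4 weeks (± 7 days). In Cohort A the next scan is due 16 weeks (112 ± 28 days) after the last on-treatment scan. That is day 84 to 140 if that scan coincides with the last dose, or day 56 to 112 if it was 28 days earlier, as after a fifth cycle. Patients who have progressed have only six-monthly survival follow-up, so no single contact covers everyone to day 183.
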